## **BACKGROUND AND SIGNIFICANCE**

Fabry disease is an x-linked lysosomal storage disease defined by a deficiency of alpha-galactosidase, leading to the accumulation of a cell membrane derived glycolipid, globotriaosylceramide, and its metabolites within the cytoplasm and lysosomes of many types of cells, including endothelial cells, cardiomyocytes, renal glomerular cells, and neurons (Clarke, 2007). Gastrointestinal manifestations such as abdominal pain, diarrhea and nausea are prominent and, although typically non life-threatening, can frequently cause significant morbidity and burden in a patient's life. Recent studies have found that up to 50% (range of 16-70%) of patients with Fabry disease, including both males and females, experience gastrointestinal symptoms (Hoffman et al., 2007). The symptoms are typically one of the first presenting signs of Fabry disease, after acroparesthesia, with the mean onset in males at age 5 years and females several years later at 9.5 years. Although females present later, the severity of the symptoms equalizes as the patient ages (Hoffmann, Schwarz, Mehta, & Keshav, 2007).

The gastrointestinal symptoms can vary in intensity and can occur anywhere along the GI tract including the stomach, small and large bowel. They tend to progress in incidence over time. The most common complaint is abdominal pain with up to one third of adults endorsing this ailment and many children reporting it as their initial GI symptom (Hoffmann et al., 2007; Mehta et al., 2004). It is typically described as a cramping mid-abdominal pain worsened with meals and increased stress. Alterations in bowel habits is the next most common GI presentation, with many patients complaining of urgent, explosive, post-prandial diarrhea frequently necessitating significant lifestyle changes. Others, mostly female, experience constipation (Hoffman, 2007). Less common, but significant gastric symptoms are also reported including nausea, vomiting and early satiety. Patients describe decreased appetite, inability to tolerate many foods and feelings of bloating consistent with gastric dysmotility.

Although the presence of gastrointestinal symptoms in Fabry's disease was first described more than 50 years ago by Van Wayjen in 1958, little remains known about the specific pathophysiology of the symptoms (Van Waygen, 1958). Few case reports have examined the histology and dysmotility affecting those with gastrointestinal symptoms with no large scale studies ever conducted. The symptoms are speculated to be caused by a combination of vasculopathy and neuropathy due to glycolipid accumulation causing ischemia leading to cellular

necrosis and also alterations in cell function resulting in a pro-inflammatory state. The effects on neurons and the nearby blood vessels, both mechanical and functional, are thought to cause dysmotility thus producing many of the gastrointestinal symptoms (Aerts et al., 2008). These pathophysiological mechanisms have been more extensively studied in other systems such as cardiac, renal and dermal, however little is confirmed in the actual gastrointestinal cell (Askari et al., 2007; Liguori et al., 2010; Simon, Frey, Gruler, & Bültmann, 1990)

Several case reports have been published examining the evaluation of patients with gastrointestinal complaints in Fabry disease. Superficial biopsies taken from the small bowel and rectum, showed normal villous architecture and normal surface epithelium under light microscopy with enlarged and vacuolated neurons and with globotriaosylceramide deposition in the neurons and nerve (Flynn et al., 1972; Friedman et al., 1984; Jack et al., 1991; O'Brien et al., 1982). The blood vessels and muscle cells of the muscularis mucosa were noted to have deposits with luxol fast blue positive material. Electron microscopy noted electron dense intralysosomal striped "zebra-like" bodies in smooth muscle and ganglion cells (Sheth et al., 1981). To our best knowledge, all the prior studies have completed analysis with only superficial biopsies, with no more than 2 patients per case series, and all have been published more than a decade ago. Furthermore, there has been no in depth quantification of gastrointestinal cellular injury or comparison to control specimens.

Additionally, there has been only one published report of the underlying functional dysmotility analysis in these patients. In 1987, Argoff et al found that 5 out of 7 patients with gastric symptoms had delay in gastric emptying scan and responded well to metoclopramide, suggesting a similar neuropathy to that seen in diabetic gastropathy (Argoff et al., 1998). Although many of the presenting gastrointestinal symptoms seem to involve dysfunction of the whole gastrointestinal tract, additional motility testing examining the small and large bowel has not been completed in these patients.

As the underlying pathology remains unclear, there is no Fabry-specified protocol for evaluation of patients with gastrointestinal symptoms. Bloodwork is frequently completed for initial evaluation of symptoms including CBC and electrolytes, which are typically normal. Additional workup including imaging such as a KUB may be performed, which is also commonly without abnormalities. In some patients with persistence of concerning symptoms, it may be clinically necessary to complete further evaluation via colonoscopy to evaluate for underlying mucosal disease.

The treatment for the GI symptoms in Fabry disease was historically symptomatic, utilizing promotility drugs, neuromodulators and antibiotics. The management has progressed recently with the initiation of enzyme replacement therapy over the past decade with many patients starting the replacement at younger ages. Although enzyme replacement therapy has shown promising results with some decrease in symptom severity, GI complaints remain a significant cause of morbidity for some patients on ERT (Banikazemi et al., 2005; Barbey et al., 2007; Zarate & Hopkin, 2008). More in depth understanding of gastrointestinal symptoms pathophysiology in Fabry disease is acutely needed in order to develop more specific evaluation of the symptoms and advance the treatment of these patients. By gaining additional insight into

the characterization of symptoms and the relationship to dysmotility, we anticipate improved and more focused adjunct therapies for the patients.

### **SPECIFIC AIMS**

#### **Primary Aim – Dysmotility**

The primary goal of the study is to gain further comprehension of the pathophysiology underlying dysfunction of the gastrointestinal tract and to correlate the abnormal findings with symptoms in an attempt to further classify the disease manifestation. This investigation will be achieved by examining the gastric, small bowel and colon emptying time. Additionally, neurologic and myopathic changes will be analyzed through evaluation of contractility, pH and temperature of the bowel as measured by the SmartPill study. These results will be correlated with the patient's subjective gastrointestinal symptoms in an attempt to elucidate a causational relationship between functional abnormalities with presentation.

The aim in this phase of the study is to gain additional understanding of the disease manifestation via motility abnormalities in order to improve symptom targeted therapy. The hypothesis is that patients with Fabry disease will have abnormal motility which will correlate with the patients symptoms and quality of life as noted on the questionnaires.

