## **Inclusion/Exclusion Criteria**

### *Inclusion Criteria:*

1. Adults ages 18- 70 years who have diagnosed Fabry disease either by enzyme testing in males or by enzyme and/or genetically confirmed mutation in females.
2. Adults with Fabry disease having any gastrointestinal complaints within the past year.
3. Endoscopic Mucosal Resection ONLY – Symptomatic subjects necessitating a sigmoidoscopy who are enzyme replacement therapy naive OR less than 6 months of treatment.

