### **Sigmoidoscopy and Endoscopic Mucosal Resection (Visit 4)**

This study visit should take about 3.5 hours to complete.

This study visit consists of a sigmoidoscopy with biopsies and an endoscopic mucosal resection. When additional workup of gastrointestinal symptoms is warranted for altered bowel habits and/or abdominal pain, a subset of 15 treatment naive patients or with less than 6 months of treatment will be recruited from those who completed the SmartPill study for a sigmoidoscopy with biopsy collection and additional endoscopic mucosal resection.

The patient will fast the night prior and receive 2 enemas the morning of the procedure. The patient will present for completion of a clinically needed sigmoidoscopy with routine rectal and sigmoid biopsy collection. In addition, an endoscopic mucosal resection will be completed in the rectum. Biopsies will be sent to pathology for the following analysis.

1. Light microscopy with hematoxylin and eosin, periodic acid schiff, toluidine blue and acetylcholine staining.
2. Electron microscopy
3. Immunohistochemistry staining with anti-Gb3 monoclonal antibody.

All specimens will be examined for cellular morphology, other significant noted injury or structural abnormalities and location of deposition. The biopsies will be specifically analyzed for vascular and neuropathic changes. The specimens will be assessed for presence or absence of neuronal swelling, myelination, vascular sclerosis, intimal fibrosis and hypertrophy of the smooth muscles of the arterioles. The neurological and vascular cells will be assessed for deposition and quantification will be determined based on a degree of deposition scale used previously for renal biopsy analysis in Fabry disease (0 No deposit, +deposit present in a few cells, ++ deposits present in some cells, +++ deposits present in many cells) (Valbuena et al., 2008). Finally, results of analysis of all specimens will be compared to healthy aged-matched controls obtained from banked specimens in the pathology department. Once the analysis is completed, results will be correlated with the patient's gastrointestinal symptom presentation.

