### **ADDITIONAL STUDY INFORMATION**

#### **Description of SmartPill**

The SmartPill GI Monitoring System includes an ingestible capsule, a receiver, a receiver docking station and display software. The capsule houses sensors for pH, temperature, and pressure, and has the ability to transmit the sensed data at 434 MHz to a receiver worn by the subject. The portable receiver worn by the subject receives and stores data; the MotiliGI software provides calculations and graphical displays to the physician. After activation and ingestion, the capsule signals are transmitted from within the GI tract and are captured by a receiving antenna incorporated into the receiver, which also provides an interface for data transmission to a PC as well as connections for battery charging. The capsule functions for at least 5 days after activation and has a pH range of 0.5 to 9 with an accuracy of  $\pm 0.5$  pH units. The pressure sensor has a pressure range of 0 to 350 mm Hg with an accuracy of 5 mmHg. The temperature sensor has a range of 25° to 49°C, with an accuracy of  $\pm 0.8^\circ\text{C}$ .

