## **BIOSTATISTICAL ANALYSIS**

Descriptive statistics based on a series of 50 patients for histologic and dysmotility findings. Univariate and multivariate regression analysis of relationship between motility parameters, histologic disease state and GI symptoms in Fabry patients.

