## **POTENTIAL BENEFITS**

There is no direct benefit to healthy subjects for participation in this study. Results from the study will help to further understand the disease and possibly lead to better diagnosis and treatment of gastrointestinal symptoms in patients with Fabry disease in the future.

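### The first half of the primary hypothesis, that motility is abnormal, is described but never tested against a reference, so some abnormal values can look like confirmation

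*Combined protocol and SAP*

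**What the plan says.** The Primary Aim – Dysmotility section states a two-part hypothesis: "patients with Fabry disease will have abnormal motility which will correlate with the patients symptoms". The study pursues it by "examining the gastric, small bowel and colon emptying time", with contractility, pH and temperature as further capsule measures. No cut-off is given for any of these.

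The Biostatistical Analysis section has two sentences. The first is "Descriptive statistics based on a series of 50 patients for histologic and dysmotility findings". The second is "Univariate and multivariate regression analysis of relationship between motility parameters, histologic disease state and GI symptoms in Fabry patients".

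Inclusion criterion 2 limits entry to "Adults with Fabry disease having any gastrointestinal complaints within the past year", so every motility subject is a symptomatic Fabry patient.

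Controls appear only for tissue: "Finally, results of analysis of all specimens will be compared to healthy aged-matched controls obtained from banked specimens in the pathology department". The Potential Benefits section says "There is no direct benefit to healthy subjects for participation in this study", but no healthy group is recruited or analysed anywhere in the plan. The device description says that "the MotiliGI software provides calculations and graphical displays to the physician" and cites no normal values.

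The Power section expects 35 of 50 patients to have delayed gastric emptying. This rests on an earlier report in which 5 of 7 Fabry patients with gastric symptoms had a delay. The section uses the words abnormal and delayed without defining either.

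**The concern.** Abnormal has meaning only relative to normal. The within-Fabry regression can address the second half of the hypothesis, whether motility tracks symptoms. It cannot address the first half, because it has no reference point outside the cohort.

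Any reference limit leaves some healthy people outside it, and three transit times give three chances to fall outside. Some patients will therefore be labelled abnormal whatever the truth is, and the plan compares their number with nothing. The Secondary Aim – Protocol section intends to build guidance for caregivers on the dysmotility findings, so an unsupported statement that Fabry motility is abnormal would carry forward. The hypothesis is also worded for Fabry patients in general, although only symptomatic ones are studied.

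**Working it through.** **1. The plan's own figure.** The Power section starts from 25 patients with a symptom association and divides twice by 70%: 25/0.70 = 35.7 (stated as 35), then 35/0.70 = 50. The 50 reproduces. The chain contains no null rate, alpha or effect size, so it is recruitment arithmetic and not a test of abnormality. The source proportion, 5/7 = 71%, has an exact 95% interval of 29% to 96%.

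**2. What healthy motility would produce.** The cohort size of 50 and the three transit times come from the protocol. The documents do not give the share p of healthy people outside each limit, so p = 5% and p = 10% are assumptions, as is independence between segments.

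- Expected number abnormal on one transit time: 50p.
- Share abnormal on at least one of three: 1 − (1 − p)³.

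| p | One transit time | At least one of three |
|---|---|---|
| 5% | 50 × 0.05 = 2.5 of 50 | 1 − 0.95³ = 14.3%, or 7.1 of 50 |
| 10% | 50 × 0.10 = 5 of 50 | 1 − 0.90³ = 27.1%, or 13.55 of 50 |

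At p = 5%, the chance that at least one patient of 50 is abnormal on a single measure is 1 − 0.95⁵⁰ = 0.92. The chance that at least 5 of 50 are abnormal on one or more of three is 0.86. Positive correlation lowers the composite only somewhat: at correlation 0.5 and p = 5%, simulation gives about 12.5% instead of 14.3%.

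**3. Could healthy motility reach the sizing figure?** No. The binomial probability of 35 or more of 50 abnormal is about 3 × 10⁻³⁴ for one measure at p = 5%, and about 3 × 10⁻¹⁰ for any of three at p = 10%.

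**4. Is a benchmark test feasible with 50 patients?** The rule is to declare a segment abnormal if the exact (Clopper–Pearson) lower bound exceeds p. This is the same as requiring r or more of 50 with P(X ≥ r | p) no greater than the one-sided alpha.

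| Approach | p | r | One-sided alpha attained | Power |
|---|---|---|---|---|
| One primary segment, 95% interval | 5% | 7 | 0.012 | 0.90 at a true 20% |
| One primary segment, 95% interval | 10% | 10 | 0.0245 | 0.84 at 25% |
| Three segments, Bonferroni (0.025/3 each) | 5% | 8 | 0.003 | 0.81 at 20% |
| Three segments, Bonferroni (0.025/3 each) | 10% | 12 | 0.003 | 0.62 at 25%, 0.86 at 30% |

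Testing three independent segments with unadjusted 95% intervals would give a chance of at least one false declaration of 1 − (1 − 0.0118)³ = 3.5% at p = 5%, and 1 − (1 − 0.0245)³ = 7.2% at p = 10%. The nominal level is 2.5%, so some control is needed.

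**The case against.** A reader might infer that the hypothesis will look confirmed whatever the data show. The documents do not support that, for three reasons.

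- The Power section states an expectation of 35 of 50, which healthy motility would essentially never reach. A reader who holds the protocol would see 7 of 50 as far short of it.
- The hypothesis is joint. Its symptom-correlation half is analysed by regression, and chance out-of-range values would not be expected to track symptoms. Nothing says the hypothesis is judged on the descriptive share alone.
- For a single measure at 5%, only about 2.5 of 50 would be abnormal by chance, which is hardly a large share.

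All of this stands against the stronger reading, but none of it supplies the missing test. The 35 of 50 is used only to size the study. It rests on seven patients with gastric symptoms measured by gastric emptying scan, whereas this study uses a capsule in patients with any gastrointestinal complaint. It is also silent on small-bowel and colonic transit. The regression cannot show that motility differs from normal.

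It is also tempting to count contractility, pH and temperature as further chances to be abnormal and to quote an any-of-six rate. The plan defines no such composite and ties those measures to a separate question, so that figure should not be used. The any-of-three figure is likewise only an illustration, because the plan does not define that endpoint either.

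Finally, a reader might infer that the sponsor intends to generalise to symptom-free patients. Entry criteria and aims point throughout to patients with symptoms, so this part is a wording correction.

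**Conclusion.** The concern holds in a limited form. As planned, the first half of the primary hypothesis can be neither supported nor refuted. With no decision rule, a descriptive report of some abnormal values can be read as confirmation even if motility is normal; whether it would be read that way is not settled by the documents. The chance background is about 2.5 to 5 of 50 on one transit time and about 7 to 13.5 of 50 on any of three. These figures assume limits that leave 5% to 10% of healthy people outside and, for the composite, independent segments. The gap should be closed before analysis. It does not affect the symptom-association half of the hypothesis and does not call for more patients.

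**What to change.** In the Biostatistical Analysis section, before any data are analysed:

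- Name the capsule reference limits for gastric, small-bowel and colonic transit time, and the percentage of healthy people outside each.
- Report the cohort percentage outside each limit with an exact interval. Call a segment abnormal in the cohort only if the lower bound exceeds the healthy percentage.
- Choose one form of error control. Either make gastric emptying time, the parameter used under Power, the primary segment at the 95% level, or use Bonferroni-adjusted intervals across the three segments.
- Treat contractility, pH and temperature as descriptive.
- Word the hypothesis in the Primary Aim for symptomatic Fabry patients.

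The cost is text and a literature or manufacturer source: the limits and healthy rates are not in the documents and must be found elsewhere, ideally from the same capsule procedure. No extra patients or visits are needed. The downside is that a modest excess may not be declared, most clearly with Bonferroni intervals against a 10% healthy rate, where power is 0.62 at a true 25%.

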#### **Secondary Aim - Histology**

A secondary goal will be examine all aspects of histological injury including neuronal such as myelin depletion and nerve swelling, vascular such as intima thickening and cellular hypertrophy, and GL-3 deposition. This will be completed by obtaining deep specimen biopsies of the mucosa and submucosa for analysis of the histopathology of the gastrointestinal tract in symptomatic patients with Fabry disease who are treatment naive or with only <6 months of treatment.

The specimens will be obtained by a clinically warranted sigmoidoscopy and will include an additional deeper endoscopic mucosal resection. Tissue analysis will include evaluation of abnormalities of cellular structure and morphology with correlation with gastrointestinal complaints for each patient and comparison against age matched non-Fabry patient tissue. The hypothesis is that patients will have abnormal findings on histology, which will correlate with the subjects symptoms and findings of on the questionnaires.

#### **Secondary Aim – Protocol**

There is no uniform protocol for assessment and evaluation of gastrointestinal complaints in patients with Fabry disease. The aim is to create a protocol for Fabry disease caretakers to follow based on the histologic and dysmotility findings.

### **SUBJECT SELECTION**

#### **Equitable Selection of Subjects**

This study is open to all individuals, male and female, between 18 and 70 years of age who meet all of the inclusion and exclusion criteria, and have been diagnosed with Fabry disease. Women who are pregnant or nursing will not be allowed to enter the study due to unknown risk factors. Subjects who are not able to provide informed consent form themselves will not be enrolled.

## **Inclusion/Exclusion Criteria**

### *Inclusion Criteria:*

1. Adults ages 18- 70 years who have diagnosed Fabry disease either by enzyme testing in males or by enzyme and/or genetically confirmed mutation in females.
2. Adults with Fabry disease having any gastrointestinal complaints within the past year.
3. Endoscopic Mucosal Resection ONLY – Symptomatic subjects necessitating a sigmoidoscopy who are enzyme replacement therapy naive OR less than 6 months of treatment.

### *Exclusions Criteria:*

1. Fabry disease with other concomitant gastrointestinal diagnosis (Example: Inflammatory Bowel Disease, Celiac Disease)
2. Pregnancy
3. Endoscopic mucosal resection exclusions:
  - a. Any contraindication to conscious sedation,
  - b. Contraindication to endoscopy,
  - c. Untreated or unmanageable coagulopathy,
  - d. Thrombocytopenia (<50).
  - e. Patient on ERT for more than 6 months.
4. Exclusions for SmartPill:
  - a. Previous history of bezoars.
  - b. Prior GI surgery except for cholecystectomy, appendectomy, or Nissen fundoplication.
  - c. Any abdominal surgery within the past 3 months
  - d. History of diverticulitis, diverticular stricture, and other intestinal strictures
  - e. Tobacco use within eight hours prior to capsule ingestion and during the initial 8-hour recording on Day 0 or the Ingestion visit.
  - f. Alcohol use within eight hours prior to capsule ingestion and throughout the entire monitoring period (5 days).
  - g. BMI > 38
  - h. Allergies to components of the SmartBar
  - i. Use of medical devices such as pacemakers, infusion pumps, or insulin pumps.
  - j. Uncontrolled diabetes with a hemoglobin A1C greater than 10.

